# 9.1 Social and Functional Well Being

Perceived health status can be an important factor in the functional assessment for women with gynecologic disease. We plan to study overall wellness and social support as it relates to treatment in women diagnosed with VIN II/III using the following validated survey instruments:

• FACT-V: In order to assess functional health status we will use the Health Status the Functional Assessment of Cancer Therapy (FACIT) instrument specific for vulva disease called FACT-V (appendix 1.2). [16]

# 9.2 Sexual Function

Sexual function is often affected following treatment for dysplasia due to the high occurrence of scarring and discomfort associated with these procedures. We will evaluate sexual function as it relates to treatment women diagnosed with VIN II/III using the following validated survey instruments:

- Female Sexual Function Index (FSFI) validated survey instrument, (appendix 1.3) for overall sexual function. [17]
- Female Sexual Distress Survey (FSDS), a validated instrument for measuring sexual distraught (appendix 1.4) [18].

# 10. Protection Against Risks

Study staff will obtain all necessary Good Clinical Practice (GCP) and human protection HIPAA training to oblige to such standards for maintaining participant's privacy. REDCap, a secure data collection system, will be used to capture data.[19] REDCap tools provide the highest possible degree of assurance that data

will be secure. The University IT department also provides encrypted email services to internal and external recipients. Any study information communicated among the research staff will be done using the encrypted University email service.

There is a risk that subjects may feel uncomfortable answering the survey questions, particularly those regarding their sexual function. Participants will be informed that they may skip any question they feel uncomfortable answering.

#### 11. Event reporting

#### 11.1 Adverse Events

An Adverse Event [AE] is defined as any unfavorable and unintended sign (including abnormal laboratory finding), symptom, or disease temporally associated with the use of a medical treatment or procedure, regardless of whether it is considered related to the medical treatment or procedure (attribution of unrelated, unlikely, possible, probable or definite). An unanticipated event is defined as any adverse experience where the nature, severity or frequency is not described in the application form or detailed in the consent form. This can also include non-compliance issues such as over enrollment of subjects without prior COMIRB approval.

The causal relationship to study treatment will be determined by the PI and used to assess all AEs and unanticipated problems. The causal relationship can be one of the following:

**Possibly related**: In the opinion of the PI, the adverse event is unlikely to be related to the study intervention, drug or device.

**Probably related**: In the opinion of the PI, it is more likely than not that the adverse event is related to the study intervention, drug or device.

**Related to the research**: An event is "related to the research procedures" if in the opinion of the principal investigator, it was more likely than not [probably] to be caused by the research procedures or if it is more likely that not [probably] that the event affects the rights and welfare of current participants.

The PI will report any unexpected event that is deemed to be probably related or related to the research within 5 days, per COMIRB's policy.

The risks associated with the ultrasonic aspirator and the CO2 laser ablation devices are similar with the exception that early studies suggest scarring may be significantly decreased with the use of the ultrasonic aspirator. [1] Previous studies have also suggested that the ultrasonic aspirator will have less recurrence of dysplasia following treatment. [3]Since these early studies have failed to provide significant power, this is only hypothesized at this time and is the primary outcome for this phase III study.

Adverse events that are deemed not related will be documented in the study AE log, subject study charts, and reported to COMIRB at the time of annual review,

per their policy. The coordinating site will review AEs at interim analysis. Anticipated clinical adverse events may include:

- Pain and/or discomfort (~25% of women)
- Presence of scarring (~30% of women receiving CO2 laser, less than 5% in women receiving ultrasonic aspirator)
- Dysureia or burning (~25% of women)
- Adhesions (less than 5%)
- Infection: yeast, UTI, or other (~10% of women)
- Abnormal discharge (less than 10% of women)
- Eschar (~10% of women). [1]

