# 11.2 Serious Adverse Event

A Serious Adverse Event (SAE) is any untoward medical occurrence at any dose that:

- Results in death
- Is life-threatening (defined as an event in which the subject was at risk of death at the time of the event; it does not refer to an event which hypothetically might have caused death if it were more severe)
- Requires inpatient hospitalization or causes prolongation of existing hospitalization (see *NOTE*\*: below for exceptions)
- Results in persistent or significant disability/incapacity
- Is a congenital anomaly/birth defect
- Is an important medical event, defined as a medical event that may not be immediately life-threatening or result in death or hospitalization but, based on appropriate medical and scientific judgment, may jeopardize the subject or may require intervention (e.g., medical, surgical) to prevent one of the other serious outcomes listed above

Suspected transmission of an infectious agent (e.g., pathogenic or non-pathogenic) via the study treatment is an SAE.

\*NOTE: The following hospitalizations are not considered SAEs:

- A visit to the emergency room or other hospital department lasting less than 24 hours that does not result in admission (unless considered an "important medical event" or a life-threatening event)
- Elective surgery planned before signing consent
- Admissions as per protocol for a planned medical/surgical procedure
- Routine health assessment requiring admission for baseline/trending of health status (e.g., routine colonoscopy)
- Medical/surgical admission other than remedying ill health state that was planned before study entry. Appropriate documentation is required in these cases
- Admission encountered for another life circumstance that carries no bearing on health status and requires no medical/surgical intervention (e.g., lack of housing, economic inadequacy, caregiver respite, family circumstances, administrative reason)

Participants experiencing a SAE should be discontinued from the study and followed per clinical standard of care. SAEs should be documented on the AE CRF and reported to local IRB and the coordinating site within 48 hours of notification of event.

There are no known reports of serious adverse events following CO2 laser and ultrasonic aspiration for vulva dysplasia.

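### The causality scale in section 11.1 defines possibly related as unlikely, and has no level for unrelated, plausible or definite relationships

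*Combined protocol and SAP*

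**What the plan says.** Section 11.1 (Adverse Events) describes causality in two ways. Its definition of an adverse event lists five levels: "attribution of unrelated, unlikely, possible, probable or definite". It then says that the PI determines the causal relationship, that this is used for every adverse event and unanticipated problem, and that it takes one of three values:

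- For *possibly related*, the definition reads: "In the opinion of the PI, the adverse event is unlikely to be related to the study intervention, drug or device".
- For *probably related*, the PI must hold that "it is more likely than not that the adverse event is related to the study intervention, drug or device".
- For *related to the research*, the PI must hold that "it was more likely than not [probably] to be caused by the research procedures", or, at the same likelihood, "that the event affects the rights and welfare of current participants".

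Two reporting routes in the section depend on the result. The expedited one reads: "The PI will report any unexpected event that is deemed to be probably related or related to the research within 5 days", and is attributed to COMIRB's policy. The other reads: "Adverse events that are deemed not related will be documented in the study AE log, subject study charts, and reported to COMIRB", at annual review.

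Serious events have their own rules. Section 11.2 requires them to be "reported to local IRB and the coordinating site within 48 hours of notification of event". Section 11.2.1 adds 24 hours to the sponsor whether or not the event is related, section 13.1 adds 5 days to the overseeing IRB, and section 13.2 adds 5 business days to the safety monitor. Section 13.2 applies the same 5 business days to unanticipated problems and to reportable adverse events, a term it does not define.

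**The concern.** A causality scale is useful only if two assessors reading the form give the same event the same code. Here one assessor may follow the label and enter a plausible event as *possibly related*. Another may follow the definition and enter an unlikely event under the same code. The recorded value would then carry two meanings that could not be separated afterwards.

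At stake are the reliability of relatedness coding in both arms and a clear reporting route for non-serious events that might plausibly have been caused by either device. This text governs conduct: the PI is told to apply the scale to all adverse events.

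**Working it through.** The plan gives no figure on this point, so there is no arithmetic. The check places each degree of likelihood against the three definitions and the two causality-based routes in section 11.1. *More likely than not* is read as above 50%.

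| PI's actual view of a device relationship | In the five-level list? | Category under the three definitions | Route stated in 11.1 |
|---|---|---|---|
| Unrelated | Yes | None | AE log, charts, annual review |
| Unlikely | Yes | *Possibly related* | None stated |
| Plausible, but not above 50% | Yes (possible) | None fits | None stated |
| More likely than not | Yes (probable) | *Probably related* | 5 days if unexpected |
| Definite | Yes | No separate level; falls into *probably related* | 5 days if unexpected |

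1. **Label against definition.** The second row shows the contradiction. The section treats unlikely and possible as different levels, then gives one the meaning of the other.

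2. **Gaps.** Three of the five levels have no category of their own: unrelated, plausible and definite. The definite gap does no harm to reporting, because such events still meet the 5-day trigger. The unrelated gap is an inconsistency, because a route exists for a value that the list does not offer. The plausible gap matters most, because it lacks both a definition and a route.

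3. **Would correcting the definition alone change the 5-day report?** Suppose *possibly related* were redefined to mean a plausible relationship. The trigger would still name only the two higher categories, so these events would remain outside it. The definition and the trigger are separate matters, and both need attention.

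4. **What other rules catch.** Serious events in any row are expedited under sections 11.2, 11.2.1, 13.1 and 13.2 without a causality test. Unanticipated problems and reportable adverse events reach the safety monitor under 13.2. The remainder are non-serious, unexpected events handled as neither. For these, section 11.3.1 points to annual reports (if applicable) and interim or final reports, and section 13.2 puts non-reportable events in a 12-month safety report.

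5. **Effect on the analysis.** Section 14 compares the incidence of adverse events and serious adverse events between arms by chi-square and states no restriction by causality. Section 6.2 bases the sample size on recurrence. Neither uses the scale.

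**The case against.** The strongest reply is that this is a drafting slip with little consequence. Serious events are fully covered: the definition in 11.2 extends to important medical events, and 11.2.1 asks for a serious event report wherever seriousness is in doubt. Section 11.1 defines an unanticipated event by nature, severity or frequency rather than cause, so some unexpected non-serious events may reach the safety monitor that way. Monthly teleconferences (13.2, 15.1.4) and working-group meetings (13.2) discuss significant toxicities. The 5-day threshold is attributed to an IRB policy that is not in the documents and may be deliberate.

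Most of this stands, and it limits the point to the residual group above. It does not remove the contradiction or supply the missing levels. Meetings are not IRB reports, and an undefined class of reportable events is a weak safeguard.

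Three stronger readings are tempting, and the documents do not support them:

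- **The faulty definition is what keeps possible events out of the 5-day report.** The trigger sentence excludes them by itself, as step 3 of the check shows.
- **Probably related and related to the research cannot be told apart.** They share a likelihood threshold but have different objects: the first concerns the intervention, drug or device; the second concerns research procedures and adds a limb on rights and welfare. Both also lead to the same 5-day report.
- **The planned safety tables will mix unlikely with possible events.** No tabulation by relatedness is planned. The harm would arise only if one were made.

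**Conclusion.** The point holds as an internal contradiction in operative safety text, with a limited effect. Section 11.1 is wrong as written: one label carries the meaning of another level, the closed list cannot express the section's own five attributions, and no route is stated for the *possibly related* category.

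The consequence is confined to relatedness coding and to non-serious, unexpected events not handled as unanticipated problems or reportable adverse events. If such an event is treated as non-reportable, its formal route to the safety officer is the 12-month report. How many events this would involve cannot be estimated from the documents.

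The conclusion assumes that assessors apply the definitions as printed and that the CRF, which is not in the documents, carries the same three categories. If the CRF already uses the five levels, coding is protected in practice, but the protocol text still needs correcting.

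**What to change.** Rewrite the causality definitions in section 11.1 so that they match the five levels already listed there:

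- Give unrelated, unlikely and possible separate definitions, and make probable and definite distinct, so that each label agrees with its text.
- Keep relation to research procedures, with its rights-and-welfare limb, as a separate question from causation by the device.
- Reconcile the 5-day trigger and the not-related route with the corrected levels. State the route for possible events explicitly and consistently with COMIRB's policy. If that policy excludes them from the 5-day report, say so and say where they go.
- Align the CRF with the revised scale.

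The cost is protocol and CRF wording. No change to sample size or planned analysis is needed.

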# 11.2 Serious Adverse Event

A Serious Adverse Event (SAE) is any untoward medical occurrence at any dose that:

- Results in death
- Is life-threatening (defined as an event in which the subject was at risk of death at the time of the event; it does not refer to an event which hypothetically might have caused death if it were more severe)
- Requires inpatient hospitalization or causes prolongation of existing hospitalization (see *NOTE*\*: below for exceptions)
- Results in persistent or significant disability/incapacity
- Is a congenital anomaly/birth defect
- Is an important medical event, defined as a medical event that may not be immediately life-threatening or result in death or hospitalization but, based on appropriate medical and scientific judgment, may jeopardize the subject or may require intervention (e.g., medical, surgical) to prevent one of the other serious outcomes listed above

Suspected transmission of an infectious agent (e.g., pathogenic or non-pathogenic) via the study treatment is an SAE.

\*NOTE: The following hospitalizations are not considered SAEs:

- A visit to the emergency room or other hospital department lasting less than 24 hours that does not result in admission (unless considered an "important medical event" or a life-threatening event)
- Elective surgery planned before signing consent
- Admissions as per protocol for a planned medical/surgical procedure
- Routine health assessment requiring admission for baseline/trending of health status (e.g., routine colonoscopy)
- Medical/surgical admission other than remedying ill health state that was planned before study entry. Appropriate documentation is required in these cases
- Admission encountered for another life circumstance that carries no bearing on health status and requires no medical/surgical intervention (e.g., lack of housing, economic inadequacy, caregiver respite, family circumstances, administrative reason)

Participants experiencing a SAE should be discontinued from the study and followed per clinical standard of care. SAEs should be documented on the AE CRF and reported to local IRB and the coordinating site within 48 hours of notification of event.

There are no known reports of serious adverse events following CO2 laser and ultrasonic aspiration for vulva dysplasia.

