#### 4.1. Study Endpoints

Patients will be enrolled at participating centers prior to receiving treatment for their VIN II/III. Baseline assessments will include all study surveys and collection of demographic and clinical data.

Pain and scarring will be assessed within the first 6 weeks following treatment. Participants will be followed at 3, 6, and 12 months for recurrence. Participants will be discontinued from the study at time of recurrence, or at the completion of 12 months follow-up. Total participation is 12 months duration.

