# 6.3 Research Design and Duration

This study will employ a randomized controlled trial (RCT) design. This is a phase III study to determine the effectiveness of a more targeted treatment therapy for VIN II/III (comparing ultrasonic aspiration versus CO2 laser ablation). Potential participants will be identified through the gynecological clinical practices following diagnosis of VIN II/III and will be randomized (1:1) to one of the treatment therapies. Randomization will be stratified for multi-focal disease and HPV status.

Participants will be followed for 1 year following initial treatment for recurrence of vulva dysplasia. Study events will be documented on the study clinical research forms for each visit. The study will continue until 150 participants have completed procedures, which is expected to take approximately 3 years.

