#### 11.2.1 SAE Reporting

Following the subject's written consent to participate in the study, all SAEs, whether related or not related to study procedures, must be collected, including those thought to be associated with protocol-specified procedures. If applicable, SAEs must be collected that relate to any later protocol-specific procedure (such as follow-up skin biopsy).

The investigator should report any SAE occurring after these time periods that is believed to be related to study drug or protocol-specified procedure. An SAE report should be completed for any event where doubt exists regarding its status of seriousness.

If the investigator believes that an SAE is not related to study treatment, but is potentially related to the conditions of the study (such as withdrawal of previous therapy, or a complication of a study procedure), the relationship should be specified in the narrative section of the SAE Report Form.

SAEs, whether related or unrelated to the study intervention must be reported to the sponsor agent within 24 hours. SAEs must be recorded on the SAE Report Form;

If only limited information is initially available, follow-up reports are required. (Note: Follow-up SAE reports should include the same investigator term(s) initially reported.) If an ongoing SAE changes in its intensity or relationship to study intervention or if new information becomes available, a follow-up SAE report should be sent within 24 hours to the sponsor (or designee) using the same procedure used for transmitting the initial SAE report. All SAEs should be followed to resolution or stabilization.

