#### 12. Data Collection and Confidentiality

This study will obtain approval for conduct through the Colorado Multiple Institutional Review Board (COMIRB) for research involving human subjects. All patients within the Gynecologic Oncology clinic at the University of Colorado Cancer Center who meet the study criteria will be considered eligible for the study. We will not enroll any vulnerable populations as defined by ethical guidelines, but will follow participants that may become pregnant during the 12 month participation duration. Potential participants will be screened by the PI/Co-I and the research team and approached for consent. Consent will occur prior to the initiation of any study procedures at a scheduled clinic visit in the Gynecologic Oncology clinics of participating sites. Potential participants will be provided a private setting for inperson consent and will be adequately informed of the study intent, requirements, and potential risks and benefits. Patients will also be informed that any participation is voluntary and will not affect any clinical care they are to receive. Research staff providing consent will be certified in Collaborative Institutional Training Initiative (CITI) and Human Insurance Portability and Accountability Act (HIPAA) trainings for ethics and human protection. Patients will have time to review the consent and ask any questions prior to signing consent.

For secondary sites, additional approval will be obtained by the institution's local IRB.

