# 15.1.2 Subject Withdrawals

All participant documentation up until study withdrawal will be maintained and used for data analysis. In the event a participant is lost to follow-up, 3 documented attempts will be made to contact the participant to conduct an end of treatment visit. If after 3 attempts, the participant still does not return, a certified letter noting withdraw from study should be sent to the participant. The study coordinator will maintain a return receipt for such. Additionally, the study coordinator should send a self-addressed package to the participant for return of any study medications and/or study documents.

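### Section 11.2 takes any participant with an SAE, related or not, out of the study, so later recurrence and survey outcomes after a one-time procedure go unrecorded

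*Combined protocol and SAP*

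**What the plan says.** Section 11.2 of the combined protocol and SAP sets the rule: "Participants experiencing a SAE should be discontinued from the study and followed per clinical standard of care". The definition there starts "A Serious Adverse Event (SAE) is any untoward medical occurrence at any dose that" and then lists seriousness criteria. Causality is not among them, and inpatient hospitalization qualifies outside a short list of exceptions. Section 11.2.1 says that after consent "all SAEs, whether related or not related to study procedures, must be collected".

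The sections on follow-up read differently. Section 4.1 says "Participants will be followed at 3, 6, and 12 months for recurrence", and gives two ways for participation to end: "Participants will be discontinued from the study at time of recurrence, or at the completion of 12 months follow-up". Section 6.3 says "Participants will be followed for 1 year following initial treatment for recurrence of vulva dysplasia". Neither mentions an SAE.

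On data after exit, section 15.1.2 says only "All participant documentation up until study withdrawal will be maintained and used for data analysis". Its repeated contact attempts apply to women lost to follow-up. Section 8 places treatment at V1 and describes the 6-month (V4) and 12-month (V5) visits as standard of care, with colposcopy and the quality-of-life surveys. Section 14 compares recurrence rates by chi-square at each time point in a per-protocol set defined by treatment received. It has no rule for a missing recurrence outcome.

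**The concern.** A discontinuation rule usually protects a participant from further exposure. Here the exposure is one procedure, completed at V1. Leaving the study after that takes nothing away from treatment. It ends the trial's record of recurrence, FSFI, FSDS and FACT-V.

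The women affected stay in the analysis set by the treatment criterion but have no 12-month outcome, and some have no 6-month outcome either. Section 14 does not say whether they leave the denominator or count as free of recurrence. The two choices give different rates.

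The missingness could also be informative. The statistician is the only person section 7.1 describes as blinded, and the investigators deliver the assigned procedure. One SAE criterion in section 11.2, the important medical event, rests on medical and scientific judgment. A judgment made with knowledge of the arm can therefore end outcome collection.

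**Working it through.** **1. The sections side by side.**

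- Section 4.1: participation ends at recurrence or at 12 months.
- Section 6.3: follow-up lasts 1 year from initial treatment.
- Section 11.2: participation also ends at any SAE.
- Section 15.1.2: data up to withdrawal are kept and used; later data are not mentioned.

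Sections 4.1 and 6.3 cannot both be followed as written for a woman who has an SAE, no recurrence, and time left before 12 months. What she loses depends on timing. If the SAE comes before V4, both the 6- and 12-month results go unrecorded. If it comes after V4, only the 12-month result does.

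**2. The plan's own sample size.** Inputs from section 6.2: recurrence 37.5% against 15%, 80% power, alpha 0.05 (two-sided assumed, since the plan does not say), 62 per arm, plus 13 per arm in reserve.

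With p̄ = (0.375 + 0.15)/2 = 0.2625, the pooled formula is

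n = [1.96·√(2·0.2625·0.7375) + 0.8416·√(0.375·0.625 + 0.15·0.85)]² / 0.225² = 58.8, so 59 per arm.

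With continuity correction it is 68. The stated 62 lies between the two and is slightly conservative for an uncorrected chi-square test. Exact chi-square power at 62 per arm is 82.7%. The reserve is 13/75 = 17.3%, and section 6.2 assigns it to noncompliance, loss to follow-up and misclassified diagnosis. SAE exit is not named.

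**3. Size of the loss.** The documents give no SAE rate over 12 months. The range 1 to 10% is an assumption.

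- Women affected: 150 × 0.01 = 1.5, up to 150 × 0.10 = 15.
- Share of the 26 reserve places: 1.5/26 = 6%, up to 15/26 = 58%.

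Exact chi-square power for 37.5% against 15%, with the same loss in both arms and n rounded to whole women:

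| Assumed SAE loss | Reserve already spent (start at 62 per arm) | Power | Full enrolment (start at 75 per arm) | Power |
|---|---|---|---|---|
| 0% | 62 | 82.7% | 75 | about 89% |
| 5% | 59 | 81.4% | 71 | about 88% |
| 10% | 56 | 78.9% | 67 to 68 | about 86% |

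At 1% the change is a few tenths of a point from either starting figure. Power falls below 80% only near the top of the assumed range and only if other losses have used the whole reserve.

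**The case against.** The strongest reply is that the numbers are small. Section 11.2 knows of no SAEs after either procedure, the wording is *should*, and data up to exit are kept. V4 and V5 are standard-of-care visits, so the examination may well be in the medical record. Most of this stands, and it limits the size of the problem. It does not remove it. The statement about SAEs concerns events following the procedures and gives no rate for unrelated admissions over a year in women aged 18 to 89. An examination in the clinic record is not a trial outcome unless the protocol has it recorded.

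A reader might infer more than the documents support:

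- *That every such woman loses both the 6- and the 12-month outcome.* An SAE after V4 costs only the 12-month result.
- *That section 11.2 contradicts the requirement in section 11.2.1 to follow SAEs to resolution.* That is safety follow-up of the event and can continue after outcome visits stop.
- *That it contradicts section 12, where the study "will follow participants that may become pregnant during the 12 month participation duration".* This needs an uncomplicated delivery to count as untoward, which the definition does not plainly say.
- *That the rule biases the comparison between arms.* Unrelated admissions give no reason to expect a difference by arm. For procedure-related events, section 11.1 calls the device risks similar apart from scarring. A difference is possible, but nothing in the documents gives it a size.
- *That the trial becomes underpowered.* The table above shows this only at the extreme of an assumed range.

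**Conclusion.** The concern holds as one of avoidable missing data and an internal inconsistency. As written, section 11.2 ends outcome collection for any SAE, whatever its cause, when no study treatment remains to stop. It does not agree with sections 4.1 and 6.3, and section 15.1.2 leaves no route for recording later outcomes. The inconsistency and the data gap rest on the text alone.

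The size rests on assumptions: a 12-month SAE rate of 1 to 10%, equal loss in both arms, and a two-sided test. On those, at most about 15 of 150 women are affected, and power falls by about 4 points or less if the reserve is spent and about 3 points or less if it is intact. Power is the lesser reason to act. The main reason is that the protocol itself creates gaps in the primary endpoint that could depend on arm or prognosis, with no rule for handling them. The change is worth making because it costs little.

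**What to change.** Reconcile sections 4.1, 6.3, 11.2 and 15.1.2 so that collection of outcome data is separated from clinical management of the SAE. State that, unless the woman withdraws consent, recurrence findings and surveys at the already scheduled 6- and 12-month visits are still recorded after an SAE and included in the primary analysis. Clinical care of the SAE is left as it is.

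This takes a short protocol amendment with IRB approval at each site. The visits already take place as standard of care, so the added burden is some data entry and survey completion after an SAE.
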